## PRÉCIS

### Background:

- Gliosarcoma and primary CNS sarcomas are malignant brain tumors uniformly associated with poor outcome.
- There are no known effective medical therapies for these cancers.
- Sunitinib is an orally administered small molecule that inhibits signaling of multiple receptor tyrosine kinases including those known to be activated in CNS sarcomas.

### Objectives:

To determine the anti-tumor effect of sunitinib in recurrent gliosarcomas and primary CNS sarcomas as assessed by objective response rate (ORR).

### Eligibility:

- Patients with histologically proven gliosarcoma and primary CNS sarcoma at disease relapse after failing standard therapy (surgery and irradiation).
- Tumor tissue blocks or 15 unstained slides should be available
- Subjects must be  $\geq 18$  years old.
- Karnofsky performance status of  $\geq 60$ .
- Patients must have adequate organ function.
- Patients must not have received tyrosine kinase inhibitor(s) in the past.

### Design:

- This is a prospective, single institution, single arm, multi-cohort phase II study of sunitinib in subjects with recurrent gliosarcoma and primary CNS sarcoma that have failed prior surgery and irradiation (unless radiation therapy was contraindicated).
- Subjects will be classified into three cohorts: 1) Primary gliosarcoma; 2) Secondary gliosarcoma; 3) Primary CNS sarcoma. Cohort expansion will be carried out at indication of promising response.
- Sunitinib will be administered orally using a continuous schedule at 50 mg per day (with dose adjustments allowed for toxicity) for 2 weeks with 1 week off to constitute a 3-week cycle until disease progression or development of intolerable side-effects.
- Toxicity will be assessed every cycle by CTCAE version 5.0.

## 1. INTRODUCTION

### 1.1 STUDY OBJECTIVES

#### 1.1.1 Primary Objective:

To determine the anti-tumor effect of sunitinib in recurrent gliosarcomas and primary CNS sarcomas as assessed by objective response rate (ORR).

#### 1.1.2 Secondary Objective(s):

- To determine the 6-month and median progression-free survival rates.
- To determine the adverse event rate of sunitinib in patients with recurrent gliosarcoma and primary CNS sarcoma.
- To evaluate archival tumor tissue for activation of signaling pathways targeted by sunitinib to establish potential biomarkers of response.
- To perform broad unbiased molecular profiling of archival tumor tissues to identify potential novel biomarkers of response to sunitinib.
- To evaluate radiological parameters such as perfusion and dynamic contrast enhanced MRI before and during treatment with sunitinib.
- To longitudinally evaluate patient reported outcome measures using self-reported symptom severity and interference with daily activities using the MDASI-BT

#### 1.1.3 Exploratory:

- Blood will be collected to evaluate presence of and changes to circulating VEGFR2, PLGF, IL-4, IL-12, HGF, basic FGF, circulating tumors cells, endothelial progenitors, mature apoptotic endothelial cells, regulatory T cells, exhausted CD8 T cells, myeloid-derived suppressor cells (MDSC), and Th1/Th2 T cells. Immunophenotyping evaluations will be performed upon availability of tumor samples.
- To assess free-living physical activity and sleep quality (Optional).

### 1.2 BACKGROUND AND RATIONALE

This is an Investigator-Initiated Research study to evaluate the anti-tumor effect of sunitinib in subjects with sarcomas of the central nervous system.

#### 1.2.1 Gliosarcoma

Gliosarcoma, tumor classified as a rare variant of glioblastoma, demonstrates biphasic glial and mesenchymal differentiation. Primary gliosarcoma is a de novo neuroepithelial tumor that exhibits dual glial and sarcomatous components at initial diagnosis.[\[1\]](#) On occasion, glioblastoma in the recurrent setting may transition from typical glial phenotype (GFAP positive) to a tumor with reticulin rich sarcomatous-mesenchymal features (secondary gliosarcoma). These tumors are more common in men and often arise in the temporal lobes. While extra-cranial metastasis from glioblastoma is rare, gliosarcomas have a propensity to disseminate extra-cranially likely due to the sarcomatous component. Patients with gliosarcoma experience poor outcome with median survival ranging from 4 to 24 months.[\[2, 3\]](#)

**Abbreviated Title:** Ph II Sunitinib CNS Sarcomas

**Version Date:** 05-30-18

The underlying tumor biology of gliosarcoma appears to be distinct compared to glioblastoma. Frequency of *TP53* mutation is higher and only on very rare occasion EGFR amplification is present. In addition, MGMT methylation and IDH mutations are rare in gliosarcomas.[\[3\]](#) Most patients that present with gliosarcoma are treated similarly to those with glioblastoma in spite of the likely differences in tumor pathogenesis and therefore therapeutic response pattern. Treatment options for patients with recurrent gliosarcoma are extremely limited. However, gliosarcomas often possess platelet-derived growth factor receptor (PDGFR), KIT/ SCF autocrine activation loops, suggesting the potential utility of certain tyrosine kinase inhibitors.[\[4\]](#)

### 1.2.2 Primary CNS sarcoma

Primary sarcomas of the CNS are rare tumors (~1.5% of all intracranial tumors) with little known concerning the underlying biology. They are believed to arise from mesenchymal tissues within the intracranial cavity such as blood vessels, meninges, or bone. As such, these tumors are histologically similar to sarcomas of soft tissue or bone. The current WHO classification recognizes specific differentiation: fibrosarcoma, solitary fibrous tumor, chondrosarcoma, osteosarcoma, liposarcoma, inflammatory malignant myofibroblastic tumor, leiomyosarcoma, rhabdomyosarcoma, angiosarcoma, and other CNS sarcomas. Although detailed studies of these tumors are limited, reports indicate they may be in part driven by vascular endothelial growth factor (VEGF).[\[5\]](#) Treatment consists of surgical resection when accessible, followed by irradiation. There are no known effective medical therapies for primary CNS sarcomas.

### 1.2.3 Sunitinib (Sutent)

Sunitinib malate is approved multinationally for the treatment of gastrointestinal stromal tumor after disease progression on or intolerance to imatinib, advanced renal cell carcinoma, and unresectable, well-differentiated metastatic pancreatic neuroendocrine tumors (NET). Sunitinib is an orally administered small molecule that inhibits multiple receptor tyrosine kinases (RTKs), some of which are implicated in tumor growth, pathologic angiogenesis, and metastatic progression of cancer. Sunitinib was evaluated for its inhibitory activity against a variety of kinases (>80 kinases) and was identified as an inhibitor of PDGFR $\alpha$ , PDGFR $\beta$ , VEGFR1, VEGFR2, VEGFR3, stem cell factor receptor (KIT), Fms-like tyrosine kinase-3 (FLT3), colony stimulating factor receptor Type 1 (CSF-1R), and the glial cell-line derived neurotrophic factor receptor (RET). Sunitinib inhibition of the activity of these RTKs has been demonstrated in biochemical and cellular assays, and inhibition of function has been demonstrated in cell proliferation assays. The primary metabolite exhibits similar potency compared to sunitinib in biochemical and cellular assays. Sunitinib inhibited the phosphorylation of multiple RTKs (PDGFR $\beta$ , VEGFR2, KIT) in tumor xenografts expressing RTK targets *in vivo* and demonstrated inhibition of tumor growth or tumor regression and/or inhibited metastases in some experimental models of cancer. Sunitinib demonstrated the ability to inhibit growth of tumor cells expressing dysregulated target RTKs (PDGFR, RET, or KIT) *in vitro* and to inhibit PDGFR $\beta$ - and VEGFR2-dependent tumor angiogenesis *in vivo*. Sunitinib is clinically indicated for the treatment of advanced renal cell carcinoma, gastrointestinal stromal tumor.

As of October 2012, 13298 subjects (including healthy subjects, subjects with renal impairment, subjects with hepatic impairment, subjects with acute myeloid leukemia, and subjects with solid

**Abbreviated Title:** Ph II Sunitinib CNS Sarcomas

[figure not shown]
**Version Date:** 05-30-18

malignant tumors) in 89 completed or ongoing clinical studies had received at least one dose of sunitinib. Pharmacokinetic studies indicate sunitinib is able penetrate the blood-brain barrier.[6, 7]

### 1.2.5 Rationale for Exploratory Studies

Serum markers of angiogenesis: A potential mechanism for sunitinib resistance is the upregulation of alternative proteins and/or pathways that could drive tumor angiogenesis and/or growth independent of VEGF. Preclinical studies, involving RCC and non-RCC models have identified a variety of candidate proteins that may be involved in resistance to VEGF therapy. Among these proteins which stimulate angiogenesis directly or indirectly are fibroblast growth factor (FGF), hepatocyte growth factor (HGF), and placental growth factor (PlGF). We propose to explore the potential utility of these proteins as biomarkers of pharmacological and clinical activity of sunitinib in CNS sarcomas. These assays will be performed in the [name] Laboratory, DTB, NCI.

Peripheral blood immune monitoring: In addition to modulation of angiogenic activity, sunitinib also appears to regulate key anti-tumor immune response. Sunitinib has been shown to decrease the frequency of regulatory T cells (Tregs) and myeloid-derived suppressor cells (MDSCs) in metastatic renal cell carcinoma patients.[8, 9] It has been shown that development of sunitinib resistance is partly mediated by the survival of MDSCs, thereby providing sustained immune suppression and angiogenesis.[10] Sunitinib has also shown to shift T-helper cells toward a T helper 1 (Th1)-polarized response and increase the Th1 cell / T helper 2 (Th2) cell ratio. A significant decrease in the Th1/Th2 ratio was seen after sunitinib treatment in the PFS-short group in mRCC.[9, 11] Exhausted CD8+ T cells which express inhibitory receptors PD-1 and Tim-3 were found in cancer patients, and therapeutic response was correlated with decline in Tim-3+ CD8+ T cells. Peripheral blood will be collected into one 8 ml CPT tube. Peripheral blood mononuclear cells (PBMC) will be assessed using multiparameter flow cytometry for immune subsets including but not necessarily limited to CD8+ T-cells, CD4+Foxp3- T-cells, Tregs, monocyte subsets, MDSC subsets. Assessment will include functional markers, i.e. PD-1, Tim-3, CTLA-4, PD-L1, HLA-DR and/or CD40. Therefore, monitoring immune subsets in CNS sarcoma patients pre- and post-sunitinib therapy may contribute to improved understanding of sunitinib and possibly inform future studies.

Circulating Endothelial Cells (CEC) and Endothelial Progenitor Cells (CEP): CECs have emerged as a potentially useful marker to assess anti-angiogenic therapy. At least two distinct populations of CECs have been identified, bone marrow-derived CEP cells and mature CECs. CEP cells bear antigens that identify them as endothelial cells, such as VEGFR2 (Flk-1) and CD31, as well as antigens for stem cells, such as CD117, CD133, and CD34. Upon appropriate stimulation, bone marrow-derived endothelial progenitor cells migrate to the circulation, where they are referred to as CEP cells. CEP cells have been shown to infiltrate human tumors and give rise to tumor neovasculature. Further VEGFR signaling is thought to mobilize CECs which is consonant with the observation that CECs are increased in patients with active cancer. How sunitinib may affect CECs and CEPs is unclear. To explore this, pre-treated and post-treated samples will be obtained to perform CEC/CEP analyses by multi-parametric flow cytometry in the [name] Laboratory.

### 1.2.6 Rationale for The Patient-Reported Outcomes:

This study seeks to establish effective therapy for sarcomas of the CNS. We hypothesize that single agent sunitinib will result in anti-tumor activity. However, given the potential toxicity of sunitinib, it will be important to determine whether any determined anti-tumor effect is

associated with improvements in symptoms or whether a worsening of symptoms offsets the increase in survival.

Precedence for measuring “non-therapeutic” endpoints exists in oncology research. For example, Gemcitabine was approved by the FDA partially as a consequence of the decrease in pain reported in pancreatic patients who were treated, not on the basis of survival improvement which was modest, at best. There have been efforts in neuro-oncology to evaluate secondary endpoints using validated instruments as an additional indicator of benefit.

The M.D. Anderson Symptom Inventory-Brain Tumor Module (MDASI-BT) allows the self-reporting of symptom severity and interference with daily activities. The MDASI-BT has demonstrated reliability and validity in the adult primary brain tumor patient population.[12] This tool represents a modification of the widely used and validated MDASI, with particular attention to symptoms common in patients with brain tumors. The availability of validated instruments provides an opportunity to prospectively assess the impact of treatment, both positive and negative, on patients. The evaluation of symptom burden in this study will assist in finding the best possible treatment with the least toxicity.

## 2 ELIGIBILITY ASSESSMENT AND ENROLLMENT

### 2.1 ELIGIBILITY CRITERIA

#### 2.1.1 Inclusion Criteria

- 2.1.1.1 Patients must have histologically confirmed gliosarcoma (primary or secondary) or primary central nervous system sarcoma confirmed by the Laboratory of Pathology, NCI.
- 2.1.1.2 Patients must have measurable disease, defined as at least one lesion that can be accurately measured bidimensionally by MRI (or CT scan if MRI is contraindicated). See Section 6.3 for the evaluation of measurable disease
- 2.1.1.3 Patients must have failed standard therapy consisting of surgery, irradiation, and chemotherapy if indicated.
- 2.1.1.4 Age  $\geq 18$  years.
- 2.1.1.5 Karnofsky  $\geq 60\%$ , see Appendix 13.1.

#### 2.1.1.6 Patients must have normal organ and marrow function as defined below:

– leukocytes	$\geq 3,000/\text{mcL}$
– absolute neutrophil count	$\geq 1,500/\text{mcL}$
– platelets	$\geq 100,000/\text{mcL}$
– total bilirubin	within normal institutional limits
– AST(SGOT)/ALT(SGPT)	$\leq 2.5 \times$ institutional upper limit of normal
– creatinine	within normal institutional limits

OR

– creatinine clearance	$\geq 60 \text{ mL/min}/1.73 \text{ m}^2$ for patients with creatinine levels above institutional normal.
------------------------	---

**Abbreviated Title:** Ph II Sunitinib CNS Sarcomas

**Version Date:** 05-30-18

- 2.1.1.7 Patients must have the ability to understand and the willingness to sign a written informed consent document indicating that they are aware of the investigational nature of this study.
- 2.1.1.8 The effects of sunitinib on the developing human fetus are unknown. For this reason and because anti-angiogenic agents are known to be teratogenic, women of child-bearing potential and men must agree to use adequate contraception (hormonal or barrier method of birth control; abstinence) prior to study entry and for the duration of study participation. Should a woman become pregnant or suspect she is pregnant while she or her partner is participating in this study, she should inform her treating physician immediately.
- 2.1.1.9 Tumor tissue blocks or at least 10-15 unstained slides from the diagnosis should be available.
- 2.1.1.10 At the time of registration, all subjects must be removed  $\geq$  28 days from any investigational agents.

## 2.1.2 Exclusion Criteria

- 2.1.2.1 Patients who are receiving any other investigational agents.
- 2.1.2.2 Uncontrolled intercurrent illness including, but not limited to, ongoing or active infection, symptomatic congestive heart failure, unstable angina pectoris, cardiac arrhythmia, or psychiatric illness/social situations that would limit compliance with study requirements.
- 2.1.2.3 Prior use of tyrosine kinase inhibitors or VEGF inhibition.
- 2.1.2.4 Patients who are receiving strong CYP450 inducers or inhibitors are ineligible.
- 2.1.2.5 Pregnant women are excluded from this study because sunitinib has potential for teratogenic or abortifacient effects. Because there is an unknown but potential risk for adverse events in nursing infants secondary to treatment of the mother with sunitinib, breastfeeding should be discontinued if the mother is treated with sunitinib.
- 2.1.2.6 Patients with known HIV history on combination antiretroviral therapy are ineligible because of the potential for pharmacokinetic interactions with sunitinib. In addition, these patients are at increased risk of lethal infections when treated with marrow-suppressive therapy.
- 2.1.2.7 Uncontrolled hypertension ( $>150/100$  mmHg) while on antihypertensive medications.
- 2.1.2.8 New York Heart Association class II or greater congestive heart failure.
- 2.1.2.9 Serious cardiac arrhythmia requiring medication.
- 2.1.2.10 Baseline echocardiogram with ejection fraction  $< 50\%$  or  $\geq 20\%$  decrease from a prior study.
- 2.1.2.11 QTc interval  $> 500$  msec on baseline EKG.
- 2.1.2.12 Patients who require use of therapeutic doses of coumarin-derivative anticoagulants such as warfarin are excluded, although doses of up to 2 mg daily are permitted for

*Abbreviated Title: Ph II Sunitinib CNS Sarcomas*

*Version Date: 05-30-18*

prophylaxis of thrombosis. Note: Low molecular weight heparin is permitted provided the patient's INR is  $\leq 1.5$ .

#### 2.1.2.13 Previous exposure to anthracyclines.

#### 2.1.3 Recruitment Strategies

Both men and women of all races and ethnic groups are eligible for this study. Potential subjects will be identified from referrals to the Neuro-Oncology Clinic.

### 2.2 SCREENING EVALUATION

Documentation / confirmation of tumor diagnosis by the NCI Laboratory of Pathology is required prior to enrollment. Slides from the most recent pre-registration biopsy or resection must be submitted for review if the previous surgery was not performed at NIH.

Within 28 days prior to registration, the following assessments are required:

1. A complete history and neurological examination (to include documentation of the patient's Karnofsky Performance Status).
2. Vital signs, blood pressure
3. Neuro-imaging confirming tumor progression shall be performed on all patients. MRI is preferred over CT scan.
4. 12-lead ECG
5. Laboratory Evaluation:
  - a. CBC with differential, platelets, PT, PTT, INR
  - b. Total protein, albumin, calcium, phosphorus, magnesium, glucose, BUN, creatinine, sodium, potassium, alkaline phosphatase, ALT, AST, total bilirubin, direct bilirubin)
  - c. Urine or serum  $\beta$ -HCG
6. Echocardiogram
7. Assessment of concomitant medications and treatments.

### 2.3 REGISTRATION PROCEDURES

Authorized staff must register an eligible candidate with NCI Central Registration Office (CRO) within 24 hours of signing consent. A registration Eligibility Checklist from the web site (<http://home.ccr.cancer.gov/intra/eligibility/welcome.htm>) must be completed and sent via encrypted email to: NCI Central Registration Office [[contact]](mailto:[contact]).

After confirmation of eligibility at Central Registration Office, CRO staff will call pharmacy to advise them of the acceptance of the patient on the protocol prior to the release of any investigational agents. Verification of Registration will be forwarded electronically via e-mail to the research team. A recorder is available during non-working hours.

#### 2.3.1 Treatment Assignment Procedures

#### Cohorts

**Abbreviated Title:** Ph II Sunitinib CNS Sarcomas

**Version Date:** 05-30-18

Number	Name	Description
1	Primary Gliosarcoma	Patients with primary gliosarcoma
2	Secondary Gliosarcoma	Patients with secondary gliosarcoma
3	Primary CNS sarcoma	Patients with primary CNS sarcoma

## Arms

Number	Name	Description
1	Experimental therapy	Sunitinib 50 mg with ActiGraph

## Arm Assignment

Patients in cohorts 1, 2, and 3 will be assigned to arm 1.

### 2.4 BASELINE EVALUATION

All baseline evaluation procedures should be done prior to the study treatments. They do not need to be repeated if performed within 28 days prior to study drug initiation.

- A complete history and physical [including baseline blood pressure measurement and determination of Karnofsky Performance Score (KPS)] examination.
- A baseline standard NOB Gd-DPTA enhanced MRI should be performed.
- Thyroid Function Tests (and subsequently every 2 cycles)
- Urinalysis
- MDASI-BT
- Correlative Studies Blood Collection

The MDASI-BT will be completed only by the patient, unless changes in vision or weakness make this difficult. If this occurs, then the caregiver or research assistant may read the questions to the patient or assist with marking the severity number or score as described by the patient. A caregiver may complete the questionnaires as a patient proxy if the patient's deficits preclude self-report; however, this must be done at every assessment from baseline to end of treatment. Non-English-speaking patients will complete the questionnaire with the assistance of an interpreter during the clinic visit.

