### 3.4 QUESTIONNAIRES

The MDASI-BT will be utilized for this portion of the study. The instrument will be administered at baseline and then at the time of each evaluation that also includes imaging. Of note, the MDASI-BT will need to be given prior to informing the patients about the results of the imaging study. Full instruments are provided in the Appendix 13.3 In addition, information regarding demographics and treatment history will be collected as part of the larger study and used in this analysis.

The MDASI-BT consists of symptoms rated on an 11-point scale (0 to 10) to indicate the presence and severity of the symptom, with 0 being “not present” and 10 being “as bad as you can imagine.” Each symptom is rated at its worst in the last 24 hours. Symptoms included on the instrument include those commonly associated with cancer therapies, and those associated with the underlying disease. The questionnaire also includes ratings of how much symptoms interfered with different aspects of a patient’s life in the last 24 hours. These interference items include: general activity, mood, work (includes both work outside the home and housework), relations with other people, walking, and enjoyment of life. The interference items are also measured on 0 - 10 scales. The average time to complete the instrument is 5 minutes. The MDASI-BT has been translated into 18 languages, but the English language version will be

used for this study.[12] Non-English-speaking patients will complete the questionnaire with the assistance of an interpreter during the clinic visit.

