### 3.5 STUDY CALENDAR

Procedure	Screening/ Baseline	Cycle 1			Subsequent Cycles		End of treatment Visit 	Post Therapy Follow- up
		Day 1	Day 8	Day 15	Day 1	Day 15		
		+/- 3			+/- 3	+/-3		
History and PE	X	X	X		X		X	
Vital signs	X	X	X		X		X	
Performance Score (KPS)	X	X	X		X		X	X
CBC w/diff, plts	X	X	X		X		X	
Serum chemistry 	X	X	X		X		X	
Urinalysis	X							
PT/PTT INR	X							
Thyroid function tests 	X				X		X	
β-HCG (serum or urine)	X							
Blood Pressure	X	X	X	X	X	X	X	
Correlative Research Studies 		X	X		X		X	
MDASI-BT 	X						X	
Cranial MRI/CT 	X						X	
EKG/ECHO 	X							
Adverse Events 		X					→	
Concomitant Medications 	X	X			X			
Actigraphy 	X	X	X	X	X	X		
NIH Advanced	X							

*Abbreviated Title: Ph II Sunitinib CNS Sarcomas*

*Version Date: 05-30-18*

Procedure	Screening/ Baseline	Cycle 1			Subsequent Cycles		End of treatment Visit 	Post Therapy Follow- up
		Day 1	Day 8	Day 15	Day 1	Day 15		
Directives Form 								

*Total protein, albumin, calcium, phosphorus, magnesium, glucose, BUN, creatinine, sodium, potassium, alkaline phosphatase, ALT, AST, total bilirubin, direct bilirubin*

*Thyroid function tests to be done at baseline, C2D1, D1 of every other cycle and at end of treatment visit*

*Blood for correlative studies will be collected at C1D1, C1D8, C2D1 and at end of treatment visit*

*MDASI-BT to be done at baseline, at time of imaging studies throughout treatment, and at end of treatment visit*

*Response assessment to be done every other cycle within 7 days of initiation of odd numbered cycles, starting with Cycle 3 and at end of treatment visit. (Pre C1 MRI is done at screening. MRI is preferred.)*

*ECHO to be done at screening, day 1 of cycle 3 and every other cycle EKG/ECHO frequency of day 1 of the third cycle and every other cycle.*

*Adverse Event and Concomitant Medication evaluations to be documented at day 1 of each cycle and at end of treatment visit*

*ActiGraphy to be done at baseline and during cycles 1 through 6*

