#### **8.4 PATIENT-REPORTED OUTCOMES**

Received MDASI-BT forms will be checked versus the timing schedule and considered as valid if they fall within 14 days of the scheduled assessment. Compliance rates will be calculated as the number of received valid forms over the number of expected forms. Differences between groups in compliance will be tested by use of Fisher's exact test at every time point.

We will use descriptive statistics to describe how patients rate symptom severity and interference with function at each time point. Error bar graphs for each of the symptoms will be constructed at each time point. The proportion of patients rating their symptoms to be 7 or greater (on a 0-10 scale) will also be reported. We will construct individual patient profiles for each of the selected symptoms to describe the individual patients' patterns of change over time. We will calculate the mean symptom severity and mean symptom interference at the time of clinical evaluation. Estimates of differences in the mean symptom severity and mean symptom interference between responders and non-responders will be estimated in the intent to treat population. All patients with at least one valid questionnaire will be included in the analyses. Questionnaires completed at study registration will be considered baseline. All questionnaire data received after randomization will be used in the primary analyses.

Differences of at least 2 points will be classified as the minimum clinically meaningful change in the symptom severity and symptom interference measures. For example, an increase of 2 points or more would mean a moderate improvement, whereas a decrease of 2 points or more would be interpreted as moderate worsening. For individual symptoms, a rise in a symptom score means deterioration, whereas a reduced score means improvement of the specific symptom.

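### The baseline MDASI-BT may be up to 28 days old at first dose and 8.4 ties it to registration, so change from baseline can include untreated change

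*Combined protocol and SAP*

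**What the plan says.** - **Age of the baseline form.** Section 2.4 lists the MDASI-BT together with history and physical, MRI, thyroid tests, urinalysis and research blood. Of all these it says: "They do not need to be repeated if performed within 28 days prior to study drug initiation". The clock runs back from first dose.
- **Baseline in the analysis.** Section 8.4 uses another anchor: "Questionnaires completed at study registration will be considered baseline".
- **Recall period.** Section 3.4: "Each symptom is rated at its worst in the last 24 hours".
- **Schedule.** Section 3.4: "The instrument will be administered at baseline and then at the time of each evaluation that also includes imaging". Footnote 4 of the 3.5 calendar agrees: "MDASI-BT to be done at baseline, at time of imaging studies throughout treatment, and at end of treatment visit". The calendar row has no mark on C1D1, although performance status, blood tests and research blood are all taken that day.
- **First follow-up.** Calendar footnote 5: "Response assessment to be done every other cycle within 7 days of initiation of odd numbered cycles, starting with Cycle 3".
- **State at entry.** Section 2.2: "Neuro-imaging confirming tumor progression shall be performed on all patients".
- **Use of the scores.** Section 8.4 plans individual profiles of change over time and sets 2 points as the smallest meaningful change. Section 1.1.2 makes longitudinal MDASI-BT evaluation a secondary objective.

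**The concern.** A form with 24-hour recall describes one day. If that day lies up to four weeks before the first capsule, the reference value may not describe the patient who starts treatment. Every patient enters with progression confirmed on imaging, so stable symptoms over the gap cannot be presumed. The trial has one arm, so no control group can show how much of a later change would have occurred without drug.

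The two anchors can also disagree. If first dose falls more than 28 days after registration, 2.4 by implication calls for a repeat form, while 8.4 still names the registration form as baseline. No rule says how to treat a form completed in between. Section 8.4 refers to questionnaire data received after randomization, an event this trial does not have, so that sentence does not settle the matter.

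At stake is the question in section 1.2.6: whether anti-tumour effect comes with better symptoms or is offset by worse ones. The untreated part of any measured change would differ from patient to patient with the delay to first dose.

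**Working it through.** The plan gives no figure that depends on the MDASI-BT baseline, so there is nothing to reproduce. The check concerns timing.

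**Inputs**
- *g*, age of the baseline form at first dose: 0 to 28 days (2.4). The usual value is not stated.
- *f*, first dose to first on-treatment form: a cycle is 21 days, so Cycle 3 starts 2 × 21 = 42 days after first dose if no cycle is delayed. Section 6.3.5 agrees, with imaging every 6 weeks. Reading the 7-day window of footnote 5 as either side gives 35 to 49 days.
- Change threshold: 2 points (8.4).
- Rate of pre-dose change, *r*: not in the documents. Assumed range 0.1 to 0.5 points per week, in either direction.

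**Drug-free share of the baseline-to-first-follow-up interval: g/(g+f)**

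| g (days) | f = 35 | f = 42 | f = 49 |
|---|---|---|---|
| 0 (form on C1D1) | 0% | 0% | 0% |
| 7 | 16.7% | 14.3% | 12.5% |
| 14 | 28.6% | 25.0% | 22.2% |
| 28 (permitted maximum) | 44.4% | 40.0% | 36.4% |

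**Against the 2-point threshold**
- Suppose scores change steadily and reach 2 points at the first follow-up. The pre-dose part is 2 × g/(g+f). For g = 28 this is 0.8 points (0.73 to 0.89); for g = 7 it is 0.29 points at f = 42.
- With an assumed rate, pre-dose change is r × g/7. For g = 28: 4 × 0.1 = 0.4 to 4 × 0.5 = 2.0 points. For g = 7: 0.1 to 0.5 points. These figures illustrate and do not estimate; the sign may be positive or negative.

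**Which planned analyses use the baseline value**
- Individual profiles of change: yes.
- The 2-point threshold: yes, wherever it is applied relative to baseline.
- On-treatment descriptive summaries and proportions scoring 7 or more, by time point: no.
- Responder versus non-responder mean scores: only if those means are read as change.
- ORR and the stopping rules: no.

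**The case against.** **Section 8.4 is mainly descriptive.** It names no change-from-baseline estimator or test. A reader might infer that the plan formally counts untreated worsening as a sunitinib effect; the text does not support that. The problem enters only through the profiles and the threshold. The threshold has a separate defect: 8.4 calls a 2-point increase an improvement, yet also says a rise in a symptom score is deterioration.

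**The size is unknown.** This stands. The 40% holds only at the permitted maximum, and the drift rate has no source in the documents. Section 4 allows corticosteroids for raised intracranial pressure, so symptoms may improve before first dose as well as worsen.

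**The clash of anchors is hypothetical.** It needs more than 28 days between registration and first dose. Section 2.3 has registration within 24 hours of consent, with pharmacy told once eligibility is confirmed, and nothing suggests long delays. That bears on how often it would happen, but no rule excludes it. The age allowance in 2.4 applies in any case.

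**A C1D1 form is collected under different conditions.** Section 3.4 wants the form given before the patient hears the imaging result, and by C1D1 the patient will usually know the baseline scan. This is a real cost. It is partly present already, because progression must be shown on imaging before registration.

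**Two stronger readings do not hold.** A reader might infer that a 28-day-old form fails 8.4's own rule, under which forms are "considered as valid if they fall within 14 days of the scheduled assessment". That would need a scheduled baseline date tied to C1D1, and the calendar gives none: the form sits under Screening/Baseline. For the same reason the window does not cure the problem. Nor can one say that an older form is not a pre-treatment value. It is; the issue is its age.

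**Conclusion.** The point holds as a weakness in the reference value for a secondary patient-reported objective. Sections 2.4 and 8.4 use different anchors, the time from registration to first dose has no limit, and no form on C1D1 closes the gap. Change read against baseline can therefore include untreated change in either direction.

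At the 28-day maximum, 36% to 44% (nominally 40%) of the interval to the first on-treatment form is drug-free; at 7 days it is about 14%. These shares assume that Cycle 3 starts on time. Any conversion to points rests on an assumed rate of change, so the bias has no known size or sign. The change is worth making before enrolment because a missing pre-dose score cannot be recovered later.

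**What to change.** 1. Keep the screening/baseline MDASI-BT. In 2.4, 3.4 and the 3.5 calendar, add a form on C1D1 before the first dose.
2. In 8.4, replace the registration sentence with: *Baseline is the last valid MDASI-BT completed before the first dose of sunitinib; forms completed between registration and first dose are not post-baseline data.*

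**Cost.** One extra 5-minute form at a visit that already takes place, one calendar mark, and short edits to 2.4, 3.4 and 8.4. The C1D1 form will usually follow disclosure of the baseline scan, unlike the follow-up forms. Keeping the screening form allows a sensitivity check with the earlier score as reference. The difference between the two forms will mix symptom change with any effect of knowing the scan result, and should be reported as such.
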